11.3 Medical Monitoring

The Medical Monitor for the TDNCC should be contacted directly at this number to report medical concerns or questions regarding safety.

[contact]

12 EARLY DISCONTINUATION OF STUDY DRUG, WITHDRAWAL AND REPLACEMENT OF SUBJECTS

12.1 Discontinuation of Study Drug

If a subject discontinues study drug early for any reason they should be encouraged to return for an Early Discontinuation of Study Drug Visit (Refer to section 10.6). Subjects will not be withdrawn from the study and will be encouraged to complete all remaining visits and procedures.

If a subject discontinues study drug due to a related AE, the subject will be followed and treated by the Investigator until the abnormal parameter or symptom has resolved or stabilized.

12.2 Withdrawal of Subjects from the Study

All subjects are free to withdraw from participation at any time, for any reason, specified or unspecified, and without prejudice. This may include subjects who discontinue study drug early and who decline to continue to come in for the remaining study visits

Reasonable attempts will be made by the investigator to provide a reason for a subject's withdrawal. The reason for the subject's withdrawal from the study will be specified in the subject's source documents. Subjects who withdraw from the study will be encouraged to come in for a final visit as follows:

- If a subject withdraws prior to Day 6, they should come in for an Early Discontinuation of Study Drug Visit (Section 10.6).
- If a subject withdraws on Day 6, they should come in for Visit 2 procedures (Section 10.2)
- If a subject withdraws after Day 6, they should come in for Final Visit Procedures (Section 10.5)

Version 2.0 Version Date: 28 AUG 14 Page 39 of 57

12.3 Replacement of Subjects

Subjects who discontinue study drug early or withdraw from the study will not be replaced.

13 PROTOCOL VIOLATIONS

A protocol violation occurs when the subject, investigator or Sponsor fails to adhere to significant protocol requirements affecting the inclusion, exclusion, subject safety and primary endpoint criteria. Protocol violations for this study include, but are not limited to, the following:

- Failure to meet inclusion/exclusion criteria
- Significant non-compliance with study drug regimen
- Failure to perform spirometry at Day 1 or Visit 4
- Use of a prohibited concomitant medication

Failure to comply with Good Clinical Practice (GCP) guidelines will also result in a protocol violation. The lead Principal Investigator with consultation with the DSMB will determine if a protocol violation will result in withdrawal of a subject.

When a protocol violation occurs, it will be discussed with the investigator and a Protocol Violation Form detailing the violation will be generated. This form will be signed by a Sponsor representative and the Investigator. A copy of the form will be filed in the site's regulatory binder and in the Sponsor's files. The site will report the violation to their IRB in accordance with their IRB reporting requirements.

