8.2 Blinding

Study treatments will be administered in a double-blind fashion (i.e., subjects and site research staff will not know the treatment assigned, with the exception of the dispensing site pharmacist, central pharmacy, and designated TDNCC personnel. The following study procedures will be in place to ensure double-blind administration of test and control (IV gallium/placebo) study treatments:

- Randomization assignments will be stored in a secure database and appropriately protected and backed up.
- Access to the randomization code will be strictly controlled and limited to designated TDNCC study personnel. All other study personnel, investigators, and subjects will remain blinded to their study drug assignment throughout the study.
- A volume and appearance-matched placebo will be utilized.
- The site pharmacist will apply a blinded label to each one-liter bag of study drug.

The study blind will be broken on completion of the clinical study and after the study database has been locked and study results released. The site investigators will be provided with each subject's treatment assignment following completion of data analysis.

During the study, the blind may be broken **only** in emergencies when knowledge of the subject's treatment group is necessary for further patient management.

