14 DATA SAFETY MONITORING

A DSMB will be established to monitor safety throughout the study, review interim safety analyses, and to ensure the continued scientific validity and merit of the study. A DSMB Charter will be established for this protocol. Summary reports tabulating SAEs by treatment group will be provided on a quarterly basis to the DSMB. Comprehensive safety interim reports will be provided twice yearly to the DSMB and will include detailed summaries of all safety endpoints. The DSMB will recommend continuation or discontinuation of the study based on these interim reviews.

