15.1 Data Sets Analyzed

Intent-to-Treat Population: All subjects who are randomized and has study drug infusion started will comprise the intent-to-treat (ITT) population. The ITT population will be analyzed for the primary and secondary endpoint analyses and will comprise the safety population used for all safety analyses.

Per Protocol Population: Subjects in the ITT population who have no protocol violations, received no bisphosphonates or inhaled chronic antibiotics from 7 days prior to Day 1 through

Version 2.0 Version Date: 28 AUG 14 Page 40 of 57

Day 28, and received gallium infusion for at least five sequential days. The per protocol population will be used in the sensitivity analyses of the primary and secondary endpoints.

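### Section 13 allows withdrawal of randomized subjects for protocol violations without criteria, which can leave Day 28 FEV1 avoidably missing and conflicts with section 12.1

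*Protocol*

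**What the plan says.** Protocol section 13 lists examples of protocol violations and then states: "The lead Principal Investigator with consultation with the DSMB will determine if a protocol violation will result in withdrawal of a subject". No criteria follow. Two of the listed examples arise after randomization and can occur before Day 28: "Significant non-compliance with study drug regimen" and "Use of a prohibited concomitant medication". Section 7.2 bars inhaled chronic antibiotics and bisphosphonates through Day 28, so the second can arise at any time up to the primary endpoint.

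Other sections bear on the same subjects:

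- Section 12.1, on subjects who stop study drug early for any reason: "Subjects will not be withdrawn from the study and will be encouraged to complete all remaining visits and procedures".
- Section 12.2 describes leaving the study only as the subject's own choice. It asks a withdrawing subject to attend one visit at that time.
- Section 12.3: withdrawn subjects are not replaced.
- Section 14: "Summary reports tabulating SAEs by treatment group will be provided on a quarterly basis to the DSMB".
- Section 8.2: "All other study personnel, investigators, and subjects will remain blinded to their study drug assignment throughout the study".
- Section 15.1: "All subjects who are randomized and has study drug infusion started will comprise the intent-to-treat (ITT) population", and "The ITT population will be analyzed for the primary and secondary endpoint analyses". The same section defines a per protocol set limited to subjects without violations.
- Section 15.3 computes the primary endpoint from Day 1 and Day 28 FEV1 and leaves missing-data methods to the SAP.

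**The concern.** Study drug non-compliance and prohibited medication happen after randomization and can be related to how the subject is doing. Someone whose chest is getting worse is a plausible candidate for restarting an inhaled chronic antibiotic. If such a subject is withdrawn before Day 28, the trial gives up the measurement its primary analysis needs, and it does so by its own decision. The loss may be related to outcome without anyone being unblinded.

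Consulting the DSMB adds a second weakness. A body that holds safety data by arm is given a voice in which individual subjects go on supplying outcomes. Section 14 otherwise gives it safety monitoring and recommendations about the study as a whole.

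The stakes are the integrity of the ITT comparison and, to a lesser degree, the completeness of safety follow-up. Power is a minor issue.

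**Working it through.** **1. Do the sections agree?** Take a subject who stops the infusion on Day 3 through non-compliance. Section 12.1 keeps this subject in the study. Section 13 allows the subject to be withdrawn. Both apply, with opposite results. For prohibited medication, section 12.1 is silent and section 13 stands alone. In neither case does the ITT analysis need the withdrawal, since violators already drop out of the per protocol set. Between Day 6 and Day 28 the infusion is over, so withdrawal ends observation and nothing else.

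**2. When is the endpoint lost?** A withdrawn subject is offered a visit at the time of withdrawal: the early-discontinuation visit before Day 6, Visit 2 on Day 6, or the final visit after that. These visits include spirometry, but it is not a Day 28 value unless it happens to fall in the Day 28 ± 3 day window. So a withdrawal before that window loses the primary outcome and a later one does not.

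**3. The plan's own figures (section 15.7).** Inputs: 60 per arm, placebo rate 30%, two-sided 0.05, 10% attrition (60 × 0.9 = 54).

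Pooled-variance power = Φ{[d√n − 1.96√(2p̄(1−p̄))] / √(p₁(1−p₁) + p₂(1−p₂))}.

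- n = 60, 30% vs 58.3%: (2.192 − 1.376)/0.673 = 1.21, power 88.7% (unpooled 90.3%).
- n = 54, 30% vs 60%: (2.204 − 1.379)/0.671 = 1.23, power 89.1% (unpooled 90.8%).

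The stated 90% is reproduced to within about 1.3 points. The n = 54 figures use the full 0.05, because no interim alpha is stated. No figure in the plan is wrong on this point.

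**4. Power if violators are withdrawn on top of the planned 10%** (assumed counts, 30% vs 60%, pooled):

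| Extra losses per arm | 0 | 1 | 2 | 3 | 4 | 6 |
|---|---|---|---|---|---|---|
| Power | 89.1% | 88.5% | 87.9% | 87.2% | 86.6% | 85.1% |

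**5. Bias in a deliberate worst case.** Assumptions, none of them in the documents: 54 per arm, true rate 30% in both arms, k non-responders removed from gallium only, missing subjects dropped from the denominator. Expected responders per arm = 0.30 × 54 = 16.2.

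Spurious difference = 16.2/(54 − k) − 0.30. For type I error, divide this difference by the pooled standard error to get δ, then take 1 − Φ(1.96 − δ) + Φ(−1.96 − δ). The last column is a simulation of 400,000 trials, which gives 4.9% at k = 0.

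| k | Gallium proportion | Spurious difference | Type I, normal | Type I, simulated |
|---|---|---|---|---|
| 2 | 16.2/52 = 31.15% | 1.2 points | 5.2% | 5.5% |
| 4 | 16.2/50 = 32.40% | 2.4 points | 5.8% | 6.2% |
| 6 | 16.2/48 = 33.75% | 3.75 points | 6.9% | 6.8% |

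**6. The same withdrawals under another missing-data rule.** If the SAP counts missing as non-response, removing a non-responder changes nothing: 36/60 stays 60%. Withdrawing a subject who would have responded then costs that arm 1/60 = 1.7 points. The missing-data rule changes the direction and size of the error. It does not recover the measurement.

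**The case against.** The strongest reply is that section 13 permits withdrawal but does not require it, that ITT membership is fixed by section 15.1 whatever is decided, and that the missing-data method is in a SAP not shown. All of that stands. A reader might infer that the clause takes subjects out of the ITT population; it does not. At most their Day 28 value is missing.

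A reader might also infer that withdrawals will be steered by treatment arm. The documents do not support that. The lead investigator decides and is blinded under section 8.2, the DSMB is only consulted, and the only content expressly described as by arm is SAE tabulations. Nothing says arm information is passed on. Consultation could even be meant as independent oversight. Arm-informed selection is therefore a risk that the rule leaves open, not a documented event. Outcome-related selection needs no knowledge of arm.

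Three further limits stand:

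- A missed Visit 4 spirometry is also a listed violation, but there the value is already absent, so withdrawal cannot cause the loss.
- A larger shift, such as 36/57 = 63.2% in place of 36/60 = 60%, appears only with complete-case handling and three non-responders removed from one arm.
- Safety follow-up is shortened rather than abolished, since a last visit with adverse event review is encouraged.

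Finally, the overlap with section 12.1 is narrow, and its specific rule could be read as governing. But section 13 does not say so. One could also read the withdrawal in section 13 as stopping drug only; section 12, however, calls that discontinuation and keeps withdrawal for leaving the study.

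**Conclusion.** The point holds in a limited form. Section 13 gives discretion without criteria to withdraw randomized, treated subjects for violations that can follow from treatment or outcome. For violations before Day 28 this can create avoidable missing primary outcomes, it conflicts with section 12.1 in the case of early stopping through non-compliance, and the per protocol set makes it unnecessary.

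The size cannot be predicted, because the number of withdrawals and the missing-data rule are not in the document. Under the assumed one-sided, complete-case worst case with 2 to 6 removals, the spurious difference is about 1 to 4 points and type I error about 5.2% to 6.9%. Six further losses per arm would lower power from 89.1% to 85.1%. These effects are modest. The change is worth making because it costs little and no later analysis can replace an outcome that the trial chose not to collect. It should be made, but it does not put the design in doubt.

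**What to change.** Replace the withdrawal sentence in section 13 with wording such as:

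> A protocol violation does not by itself lead to withdrawal from the study; it is recorded and affects only membership of the per protocol population. Subjects whose infusion was started remain in the ITT population and are followed through Day 56, unless the subject withdraws (section 12.2) or valid consent is absent.

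Remove the DSMB from withdrawal decisions about individual subjects; its role in section 14 is unaffected. Reconcile section 13 with sections 8.7 and 12.1 on discontinuing study drug, so that a violation involving the infusion has one stated consequence. What that drug-stopping rule should be is a clinical matter and is not proposed here.

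The cost is protocol wording only. It adds no visits beyond those already scheduled and changes no sample size or power figure. If violators are followed to Day 28, no loss is added to the planned 10%, and power stays at 89.1% (pooled, 54 per arm, 30% vs 60%).

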14 DATA SAFETY MONITORING

A DSMB will be established to monitor safety throughout the study, review interim safety analyses, and to ensure the continued scientific validity and merit of the study. A DSMB Charter will be established for this protocol. Summary reports tabulating SAEs by treatment group will be provided on a quarterly basis to the DSMB. Comprehensive safety interim reports will be provided twice yearly to the DSMB and will include detailed summaries of all safety endpoints. The DSMB will recommend continuation or discontinuation of the study based on these interim reviews.

15 STATISTICAL METHODS AND CONSIDERATIONS

Prior to the analysis of the final study data, a detailed SAP will be written describing all analyses that will be performed. The SAP will contain any modifications to the analysis plan described below. Except where otherwise noted, all tests will be two-sided and statistical significance will be determined at the 0.05 level.

15.1 Data Sets Analyzed

Intent-to-Treat Population: All subjects who are randomized and has study drug infusion started will comprise the intent-to-treat (ITT) population. The ITT population will be analyzed for the primary and secondary endpoint analyses and will comprise the safety population used for all safety analyses.

Per Protocol Population: Subjects in the ITT population who have no protocol violations, received no bisphosphonates or inhaled chronic antibiotics from 7 days prior to Day 1 through

Version 2.0 Version Date: 28 AUG 14 Page 40 of 57

Day 28, and received gallium infusion for at least five sequential days. The per protocol population will be used in the sensitivity analyses of the primary and secondary endpoints.

15.2 Demographic and Baseline Characteristics

Treatment groups will be described and compared with respect to baseline demographic and clinical characteristics such as age, gender, race, ethnicity, genotype, height, weight, body mass index, microbiology, use of concomitant medications (hypertonic saline, dornase alpha, azithromycin) and pulmonary function. Continuous measures will be analyzed using t-tests and categorical variables will be analyzed using chi-square, Fisher's exact, or Cochran-Mantel-Haenszel tests

15.3 Analysis of Primary Endpoint

The primary endpoint is the difference between treatment groups in the proportion of subjects with a 5% or greater relative change from baseline to Day 28 of FEV₁ measured in liters, calculated as:

$$\frac{(Day\ 28\ FEV_1-Day\ 1\ FEV_1)*100}{Day\ 1\ FEV_1}$$

To test the null hypothesis that there is no difference between the treatment groups, a two-sample test of proportions will be performed adjusted for baseline FEV₁ strata. The difference between treatment groups will be provided with associated 95% CI. Additional analyses of the relative change in FEV₁ through Day 56 will include the development of a mixed-effect model for repeated measures (MMRM). Adjusted means and 95% CIs will be presented for each visit. Treatment comparisons of the average response at each visit will be generated within the MMRM model based on the linear contrast of the average using the estimated least square means (LSMeans) at Days 14, 28, and 56.

Missing data methods will be described in the SAP.

15.4 Analysis of Secondary Endpoints

Summary statistics (mean, standard deviation, median and range) of lung function parameters, sputum density, CFRSD-CRISS, and blood inflammatory markers for each visit and changes from baseline will be presented by treatment group. Descriptive statistics will be used to summarize the proportion of subjects initiating acute antibiotics (by route) and differences in proportions between the study arms will be estimated with accompanying 95% CIs.

Changes in lung function parameters (FVC in liters, FVC % predicted and FEV₁ % predicted), sputum bacterial density, CFRSD-CRISS, and inflammatory markers will be analyzed using MMRM. Adjusted means and 95% CIs will be presented for each visit. Treatment comparisons of the average response at each visit will be generated within the MMRM model based on the linear contrast of the average using the estimated LSMeans at Days 14, 28, and 56.

A log transformation will be used in all analyses of quantitative sputum culture counts and blood inflammatory markers. Change in bacterial density will include only those subjects with the pathogen at baseline. Additional descriptive analyses will be performed to summarize the disappearance and emergence of the pathogens and their susceptibility to gallium.

Version 2.0 Version Date: 28 AUG 14 Page 41 of 57

For those subjects randomized to receive IV gallium, we will determine of the Css and $t_{1/2\beta}$ by analyzing Days 1, 6, 14, 28 and 56. Clearance will be determined as the ratio of the infusion rate to the steady state concentration immediately prior to completion of the infusion. The $t_{1/2\beta}$ will be determined as 0.693/K where K is the elimination rate constant determined by the slope of the concentration/time curve after the infusion has been discontinued. To avoid unblinding, samples will only be assayed at the end of the completion of the trial.

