PK data has been determined in 9 patients receiving 100 mg/m²/day and 10 patients receiving 200 mg/m²/day in the Phase 1b study (the PK samples for one subject were lost). Steady state concentrations were achieved by 48 hours after initiation of the infusion. As shown in **Table 1**, there was no apparent increased in the gallium serum or sputum concentration area under the concentration time curve (AUC) with the increased dose. The clearance (Cl) was significantly increased with the higher dose due to increases in both renal and non-renal clearance. The lack of effect of dose on serum and sputum concentrations may reflect the uptake of gallium by white blood cells (WBC). The elimination half-life ($t_{1/2\beta}$) determined as the ratio of Cl and the elimination rate constant (K) reflects a prolonged elimination from a depot compartment.

[figure not shown]
Table 1: Pharmaco	kinetics of Galium	(mean ± standard devia	tion) .	C _{48hr} : steady
state concentration	at 48 hrs; C _{61hr} :	steady state concentration	at 61	hrs; $T_{1/2\beta}$:
elimination half -life	; Fe: Fractional excr	etion; CI: clearance .		,

	,	,	
	100 mg/m ² /day	200 mg/m ² /day	Р
SERUM	N = 9	N = 10	
C _{48hr} (μg/mL)	2.6 ± 0.6	2.3 ± 1.0	0.35
C _{61hr} (µg/mL)	2.1 ± 0.6	2.2 ± 0.6	0.79
T _{1/2β} (hr)	105 ± 14	129 ± 44	0.16
AUC (ug/mL ·hr)	503 ± 98	537 ± 153	0.59
Cl (L/hr)	3.8 ± 1.0	7.2 ± 2.1	0.0011*
(L/hr/m ²)	2.1 ± 0.4	4.0 ± 1.1	0.007 *
Fe (%)	0.19 ± 0.07	0.20 ± 0.0 9	0.67
CI _{renal} (L/hr)	0.71 ± 0.29	1.35 ± 0.52	0.0077*
CI _{nonrenal} (L/hr)	3.0 ± 0.9	5.8 ± 2.2	0.0 052*
SPUTUM			
C _{max} (μg/mL)	0.92 ± 0.73	1.11 ± 0.80	0.61
AUC (ug/mL ·hr)	480 ± 397	567 ± 518	0.69

Version 2.0 Version Date: 28 AUG 14 Page 16 of 57

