5.2 Secondary Endpoints

- Difference between treatment groups in safety parameters including the incidence of AEs, changes in clinical safety labs, and hospitalizations through the end of follow-up
- Difference between treatment groups in the change in pulmonary function parameters from baseline through end of follow-up including relative change in FEV₁ (liters), absolute change in FEV₁ (liters) and in FEV₁ % predicted, and change in FVC (liters and % predicted)
- Difference between treatment groups in the change in sputum *P. aeruginosa* density based on quantitative cultures from baseline through end of follow-up
- Difference between treatment groups in the emergence of other CF pathogens, including gallium-resistant *P. aeruginosa*, from baseline through end of follow-up
- Difference between treatment groups in the change in the CFRSD-CRISS from baseline through end of follow-up
- Determination of the steady state concentration (Css) and elimination half life $(t_{1/2\beta})$ in those subjects receiving IV gallium
- Difference between treatment groups in the change in blood inflammatory markers from baseline through end of follow-up
- Difference between treatment groups in the rate of antibiotic usage including IV, oral, and inhaled for an acute indication from baseline through end of follow-up
- Longitudinal trends in clinical features and CF pathogens following treatment through the CF Foundation National Patient Registry

Version 2.0 Version Date: 28 AUG 14 Page 22 of 57

Protocol Number: GALLIUM-IP-13 Confidential

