9.3 Pharmacokinetic Measurements

Because of limited correlation between clinical efficacy and PK measurements done in the previous Phase 1b study in CF, only limited PK assessments will be made. Expectorated sputum and blood (plasma) for determination of concentrations of gallium and iron will be collected predose and post-dose as detailed in the Table below:

PK Collection Day	Blood	Sputum
Day 1	 Pre-dose 	1 hr (+/- 10 minutes)
	• 1hr (+/- 10	post infusion start
	minutes) post	
	infusion start	

Version 2.0 Version Date: 28 AUG 14 Page 30 of 57

PK Collection Day	Blood	Sputum
Day 6	Prior to infusion stop	Prior to infusion stop
	(+/- 10 minutes)	(+/-10 minutes)
Day 14	At visit	At visit
Day 28	At visit	At visit
Day 56	At visit	At visit

The blood will be processed for plasma as detailed in the Study Laboratory Manual. All specimens will be labeled and placed immediately into a -70°C freezer. All frozen specimens will be shipped at the specified time frames, as detailed in the Study Laboratory Manual, throughout the study to a central laboratory.

Gallium and iron concentrations will be measured using inductively coupled plasma mass spectrometry (ICP-MS) done at a central laboratory.

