Serum Chemistry and Hematology Performed at Site Lab	x			
Blood Collection for Gallium and Iron Levels		X ^f	Χ ^f	
Blood Collection for Cytokines and Chemokines		Х		
Pregnancy Test (urine or serum)	х	х		
Urine Collection for Urinalysis at Performed Site Lab	х			

Version 2.0 Version Date: 28 AUG 14 Page 55 of 57

Task/Procedure	Visit 1 ^a (-1 to -6 days)	Visit 1 Day 1		Visits 2 – Visits 5 & Early Discontinuation of Study Drug
	Screening	Pre-Dose Baseline	Post- Dose	Refer to Combined Screening/Baseline Schedule of Events
Collect Expectorated Sputum for Microbiology		X ^g		
Collect Expectorated Sputum for PK			Xa	
Randomize subject		Х		
Obtain Venous Access		Х		
Study drug administration ^K			START	
Six-Hour Observation			Х	
Dispense Subject Diary ^m			Х	

^a Screening may occur on the morning of Day 1 prior to start of study drug. In this case, Screening, Baseline and Start of Treatment (Day 1) occur on the same day. Alternatively, Screening and Baseline/Day 1 may be separated into two visits as long as Screening takes place within 7 days of Baseline/Day 1.

Version 2.0 Version Date: 28 AUG 14 Page 56 of 57

^b Visit 2 should be scheduled at approximately the same time as Visit 1 as the study drug should be stopped at approximately the same time of day as it was started.

^c Subjects who withdraw from the study should be encouraged to come in for final visit procedures as described in section 12.2.

^d Subjects who discontinue the study drug early, should be encouraged to come in for the Early Discontinuation of Study Drug Visit (Section 10.6) and then proceed with all the remaining study visits. At Visit 2, perform all study procedures except for stopping the study drug administration, dispensing the subject diary, and collecting/counting returned study drug supplies (as these procedures will be performed as part of the Early Discontinuation of Study Drug Visit).

^e The CFRSD-CRISS diary will be completed daily from Day 1 through Day 6 and then again at Visits 3, 4, and 5.

f Day 1 blood for gallium and iron levels: pre-dose, and 1 hour (+/- 10 minutes) after initiating study drug infusion and Day 1 expectorated sputum for gallium and iron levels: 1 hour (+/- 10 minutes) after initiating study drug infusion.

^g Day 6 blood and sputum for gallium levels: prior to infusion stop (+/- 10 minutes)

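### Does section 15.4 go wrong by computing clearance from a single Day 6 level that it calls steady state?

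*Protocol*

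**What the plan says.** Section 15.4 fixes the formula: "Clearance will be determined as the ratio of the infusion rate to the steady state concentration immediately prior to completion of the infusion". It takes the half-life as 0.693/K, with K from the slope after the infusion stops. Section 5.2 lists "Determination of the steady state concentration (Css) and elimination half life" as a secondary endpoint in the gallium arm. Clearance is not on that list.

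Section 8.3.5 sets one dose, 200 mg/m²/day for five days. Section 9.3 explains that "only limited PK assessments will be made", because PK and efficacy were only weakly related in Phase 1b. During the infusion, blood is drawn early and at the end. Appendix 1 has "Day 1 blood for gallium and iron levels: pre-dose, and 1 hour (+/- 10 minutes) after initiating study drug infusion", and the next sample is at infusion stop on Day 6. The Day 3 contact is a phone call (section 4.1).

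The background on Phase 1b is in section 1.2. It reports "Steady state concentrations were achieved by 48 hours after initiation of the infusion". It also reports "no apparent increased in the gallium serum or sputum concentration area under the concentration time curve (AUC) with the increased dose", and states that clearance was significantly higher at the higher dose.

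**The concern.** Rate over concentration is a drug's clearance without qualification only if the level is at steady state and clearance does not vary. If both held, it would equal dose over total AUC. In Table 1 the two differ about two-fold at each dose.

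Two explanations are possible. The level may still have been rising because gallium was entering a slow depot; in that case the steady-state label would be wrong. Or the level was flat and clearance changes with rate or time; then the label is fair, but the ratio describes only the infusion period. With one blood sample after the first hour of infusion, this trial cannot tell them apart. At stake is a listed PK endpoint reported as steady state without a check inside the trial, next to a clearance that a reader might take to describe the whole exposure.

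**Working it through.** **Inputs** (section 1.2, Table 1, cohort means ± SD; 100 then 200 mg/m²/day):
- C48h 2.6 ± 0.6 and 2.3 ± 1.0 µg/mL
- C61h 2.1 ± 0.6 and 2.2 ± 0.6 µg/mL
- half-life 105 and 129 h
- AUC 503 and 537 µg/mL·h
- reported clearance 2.1 and 4.0 L/h/m²
- infusion 120 h, so 500 and 1000 mg/m² in total, at rates of 100/24 = 4.17 and 200/24 = 8.33 mg/h/m²

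**1. Reproduce the reported clearance.** Rate/C61h is 4.17/2.1 = 1.98 and 8.33/2.2 = 3.79. A mean of individual ratios exceeds a ratio of means by about 1 + CV². This gives 1.98 × [1 + (0.6/2.1)²] = 2.15 and 3.79 × [1 + (0.6/2.2)²] = 4.07, within 3% of 2.1 and 4.0. The 48-hour level with the same correction gives 1.69 and 4.31, which fits less well. The Phase 1b figure is therefore consistent with the section 15.4 formula applied to the later on-infusion level.

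**2. Compare with dose/AUC.**

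| Dose (mg/m²/day) | Rate/C61h | Dose/AUC | Ratio |
|---|---|---|---|
| 100 | 1.98 | 500/503 = 0.99 | 2.00 |
| 200 | 3.79 | 1000/537 = 1.86 | 2.03 |

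Equivalently, reported clearance × AUC is 2.1 × 503 = 1056 against 500 mg/m² given, and 4.0 × 537 = 2148 against 1000. If the AUC was truncated, the full AUC is larger and the gap widens.

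**3. Does the gap show that the level was not a plateau?** No. Held flat at C61h for 120 h, the level gives an AUC of 252 and 264, which is 50% and 49% of the reported AUC. A tail at the Table 1 half-life, C61h × t½/ln 2, adds up to 318 and 409, for totals of 570 and 673 to infinity. Cut at 336 h (an assumed window), the totals are 494 and 545. The reported 503 and 537 are close to the truncated totals and below the full ones. A flat level can therefore fit the AUC, depending on a window that the documents do not state.

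A level that went on rising could fit too. Rate/C would equal dose/AUC at a Day 6 level of 503/120 = 4.19 or 537/120 = 4.48 µg/mL. The documents give no 120-hour level.

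**4. What direct evidence is there on the plateau?** From 48 to 61 h the means went from 2.6 to 2.1 and from 2.3 to 2.2. Neither rises. At this trial's dose the change is about 4%, and the Day 6 sample comes some 59 h after the later of those times.

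**5. Could the planned samples give a better clearance?** Dose/AUC would need the on-infusion AUC, and no blood is drawn between 1 h and about 120 h. Assume a Day 6 level of 2.2. A linear trapezoid over those 119 h runs from 119 × (0 + 2.2)/2 = 131, if the 1-hour level is near zero, to 119 × 2.2 = 262, if it is already 2.2. That two-fold spread is as large as the gap in question.

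**6. Half-life wording.** Section 1.2 describes the half-life as "determined as the ratio of Cl and the elimination rate constant (K) reflects a prolonged elimination from a depot compartment". Clearance over K has units of volume, while Table 1 gives hours. This is a slip in the background text. Section 15.4 states the usual 0.693/K.

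**The case for a change.** The strongest case for a change is that the protocol itself fixes both the formula and the label, so the SAP has not simply been left to choose them. Under either explanation one term needs qualifying, and doing so costs a few words. A one-compartment drug with a 129 h half-life would reach only 1 − 2^(−120/129) = 48% of steady state at 120 h.

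Part of this stands. The trial cannot confirm a plateau from its own data, and the ratio should not be read as an average over the whole exposure.

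The rest carries less weight. The one-compartment model also predicts a rise of over 20% from 48 to 61 h (23% to 28% of steady state at a 129 h half-life), where Table 1 shows a small fall, so it is a poor guide here. The protocol nowhere claims one constant clearance; section 1.2 says the opposite. With a single dose, dependence on dose does not make the ratio wrong at that dose. The suggested relabelling keeps the same ratio and the same Day 6 value. An AUC-based alternative is unreliable for the reason in step 5. Reconciling a completed Phase 1b table would not alter this trial's analysis. An extra on-infusion sample could test the plateau, but section 9.3 gives a reason for keeping PK limited, and that is a fair trade-off for endpoints this far from the trial's purpose.

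**Conclusion.** The arithmetic behind the concern is right: in Phase 1b, rate over the 61-hour level is 2.00 and 2.03 times dose over AUC. It does not show that section 15.4 is wrong. The formula is the standard one for an infusion, it matches Phase 1b, and its steady-state premise rests on a stated result supported by nearly flat means at this trial's dose.

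A careful analyst will describe the Day 6 value as an end-of-infusion level, with the plateau taken from Phase 1b, and the ratio as an apparent on-infusion clearance. That is a matter of reporting and leaves every number as planned.

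The size of any Day 6 discrepancy is unknown. It would be about two-fold at this trial's dose if the level stays near 2.2 to 2.3 µg/mL, and nil at about 4.5. This rests on ratios of cohort means from 9 and 10 subjects and on an AUC whose window is not stated. Clearance is not a listed endpoint, and no efficacy analysis, safety analysis, sample-size figure or decision in the protocol depends on it. No change is needed.
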